### 9.6.2. Definition of data extraction algorithm

Based on the relevant diagnostic codes and key words (for free text search), a data extraction algorithm will be constructed for each event based on the consensus of the data providers. This data extraction algorithm will then be implemented by all databases.

### 9.6.3. Event data extraction

Subsequently, each database extracts data locally and transforms them into a simple common data model, i.e. standardized patient, drug and event files linkable via a patient unique identifier.

### 9.6.4. Benchmarking of incidence rates of events

For each endpoint and covariate we benchmark database-specific incidence rates (IRs) using Jerboa®, scripts will be generated by Erasmus MC. The observed IRs are compared with IRs estimated from previous database studies and literature. Outliers are identified and further investigated in an iterative manner.

We have used this multi-step process successfully in several other European multi-database projects. It maximizes the involvement of the data providers in the study by utilizing their knowledge on the characteristics and the process underlying the data collection.

After completion of harmonization, output tables for calculation and analysis of study endpoints will be created by the local data processors using the following steps (see Figure (9.6.4) 1).

Figure (9.6.4) 1 - Process to be followed by local data processors

### 9.6.5. Data elaboration

A standardized Jerboa® script and instructions will be created by Erasmus MC to create the study specific output tables. This will be double coded in Jerboa (JAVA) and SAS (version 9.2).

### 9.6.6. Missing data

Since the underlying data represent attended medical care we assume that absence of information of clinical events means absence of that condition. Lack of information on smoking, and alcohol use may occur, but this is unlikely differential.

### 9.6.7. Data sharing

A study-specific folder on the central Octopus remote research environment (RRE) for secure access by members will be used to analyze the output provided by Jerboa®. These output files will contain only anonymized de-identifiable data that will be shared in the RRE where members will have a secure and restricted access and where data will be analyzed. SAS, version 9.2, will be used for post-processing of data.

## 9.7. Data analysis

Below the main statistics will be described, a detailed statistical analysis plan will be prepared after PRAC approval of protocol.

### 9.7.1. Statistical elements

Categorical data will be presented in counts (n) and proportions (%) with 95% confidence intervals (95% CIs). 95% CIs will be calculated using the normal or Poisson distribution.

For continuous data, number of observations (n), number of patients with missing information (if applicable), mean, and standard deviation will be reported for normally distributed variables. Median and inter-quartile range will be presented for non-normally distributed continuous variables.

For the comparison of groups Chi-square, independent samples T-tests and Wilcoxon tests will be used to test for differences in categorical, normally distributed and non-normally distributed continuous variables respectively.

Analyses will be performed for the overall eligible population but also after stratification by gender, period, and presence/absence of (contra) indications, when applicable/relevant.

Effectiveness of RMM will be assessed using interrupted time series analyses.

Nested case-control analyses will be done using conditional logistic regression.

### 9.7.2. Effectiveness of the RMM

#### 9.7.2.1. Utilization of Strontium ranelate

##### *Utilization patterns population level*

*Incidence of SR* use will be calculated by dividing the number of new users in each month of the year by the amount of population person-time in each month. A new user is defined as a person without a prescription for SR in the 365 days prior to the index prescription.

*Prevalence of SR* use will be calculated by dividing the number of patients who have at least one day of SR use in a specific time unit (month or year) by the amount of population person-

time in that time unit (Note person-time is used rather than the number of persons due to the dynamic character of the underlying population).

Prevalence and incidence of SR use in each of the data sources will be calculated with their 95% CIs calculated assuming a binomial and Poisson distribution respectively. All estimates will be stratified by time (month, period and calendar years) as well as by country (database), age and sex and country.

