## 6. MILESTONES

Milestone	Planned date
Protocol submission to EMA	by 30 June 2014
Protocol approval by EMA	March 2015 *
Contract signature for study roll-out phase	April 2015*
Registration in the EU PAS register	April 2015*
Start of data collection	April 2015*
Statistical Analysis Plan	May 2015
End of data collection	End of June 2015
PSUR Update 1	October 2015
Start of data collection (second wave)	April 2016
End of data collection (second wave)	End of June 2016
PSUR Update 2	October 2016
Start of data collection (third wave)	April 2017
End of data collection (third wave)	End of June 2017
PSUR Update 3	October 2017
Final report of study results	End of November 2017

*\*Delay will impact the subsequent dates*

Milestones have been planned to maximise the efficiency and availability of data retrieval from the different data sources. A summary of such information is provided here:

Data source (Country)	Periodicity of updates	Time of the year when updates are released	Data availability for each update
SIDIAP (Spain)	Yearly	April-May	End (December 31 st ) of previous calendar year
IPCI (NL)	Yearly (twice is possible)	April-May	Variable as GPs provide not all at same time
THIN (UK)	Three times per year	Irregular	Variable as GPs provide not all at same time
HSD (Italy)	Every 6 months	June and December	End of previous calendar year (in June); up to June in December.
AUH (Denmark)	Yearly	May	December 31st the previous year

Both national regulations and prescribing practices have changed throughout the participating databases in recent months. As a consequence, in Italy, where GPs in primary care are not allowed anymore to initiate or renew strontium ranelate treatment since December 2013, the number of incident strontium ranelate users in the assessment period is expected to be null or very low. This point will be assessed for the first PSUR update (October 2015) as part of the analyses of the utilization patterns at population level (see [section 9.7.2.1](#)).

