### 7.2. Regulatory action

In the frame of 13th PSUR assessment, data submitted raised concern regarding cardiovascular safety beyond the already recognized risk for venous thromboembolism. Analysis of pooled data from randomized studies in around 7,500 post-menopausal women with osteoporosis showed an increased risk of myocardial infarction with Protelos/Osseor as compared with placebo (1.7% versus 1.1 %), with a relative risk of 1.6 (95% CI, 1.07 to 2.38), and an increased risk of venous thrombotic and embolic events — 1.9% versus 1.3 % with a relative risk of 1.5 (95% CI, 1.04 to 2.19).

As a result of this assessment, an increased risk for serious cardiac disorders, including myocardial infarction has been identified and risk minimization measures specifically targeting this identified risk were recommended by the CHMP. These risk minimization measures included a restriction of the target population by excluding patients with established, current or past history of ischaemic heart disease, peripheral arterial disease and/or cerebrovascular disease and/or uncontrolled hypertension, and restricting the indication to severe osteoporosis in postmenopausal women at high risk for fracture to reduce the risk of vertebral and hip fractures and the treatment of severe osteoporosis in adult men at increased risk of fracture. Patients with significant risk factors for cardiovascular events (e.g. hypertension, hyperlipidaemia, diabetes mellitus and smoking) should only be treated with strontium ranelate after careful consideration. In addition, strontium ranelate therapy should only be initiated by a physician with experience in the treatment of osteoporosis. These changes were disseminated in the form of a DHPC in May 2013.

In view of this newly identified risk of serious cardiac disorders, an overall benefit/risk review under Article 20 of regulation (EC) No 726/2004 started in May 2013 and was finalized on 20 February 2014 ([EMA/112925/2014, 2014](#)). This led to a restriction of the indication to patients (postmenopausal women and men) with severe osteoporosis at high risk of fracture for whom treatment with other medicinal products approved for the treatment of osteoporosis is not possible due to, for example, contraindications or intolerance. As part of RMM, a new DHPC was disseminated in March 2014.

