#### NEW INDICATIONS OF USE

Regarding the new restrictions, some of these criteria are not directly captured in the databases. Thus, operational definitions are proposed using some proxies which could lead to some misclassification or underestimation of the new restrictions. Therefore, some validation or refinement steps based on data availability and quality are required and will be further discussed with each of the academic partners before data extraction; for instance through feasibility assessed on a random sample.

- *A physician with experience in the treatment of osteoporosis.* The operational definition for this in our data sources will be:
  - Therapy initiation in secondary care settings (where available: Aarhus Database)OR
  - Therapy initiation in primary care by a physician with a “high number” of patients diagnosed with osteoporosis or on anti-osteoporosis treatment under his/her care. As both national regulations and prescribing practices have changed throughout the participating databases in recent months (e.g. general practitioners are not allowed to either initiate or prescribe repeat prescriptions of SR in Italy, different to Spain, where GPs cannot initiate but can issue repeat prescriptions of the drug), the definition of “high number” of patients with a diagnosis or treatment for osteoporosis will be based on national figures: a GP will be classified as “experienced” (with a high number of osteoporotic patients) if the number of patients with a diagnosis or treatment for osteoporosis registered with him/her is above a discriminant threshold; for instance, in the top quartile (percentile 75 or above) in the same country/data source.
- *Initiation of SR therapy not in first line,* will be operationalized as:
  - Previous use of other anti-osteoporosis drugs at any time before SR therapyOR
  - History of any formal contra-indications or precautions for the use of oral bisphosphonates (according to SmPC for alendronic, risedronic and ibandronic acid) not recognised as contra-indications or precautions for the use of SR [Appendix 14.3] at any time before SR therapy.

- Use of SR for the treatment of severe osteoporosis, will be operationalized as:
  - History of a previous osteoporotic fracture [Appendix 14.3.2] (at any time before SR therapy initiation).
- OR

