**Table (9.4) 1 - Overview of contributing databases**

Country	Netherlands	United Kingdom	Denmark	Italy	Spain
Name of the database	IPCI	THIN	Aarhus	HSD- Thales	SIDIAP
Type of database	MR	MR	ADM	MR	MR
# patients, millions	1.2	3.5	1.8	1.5	5.1
Age categories	All	All	All	>15 years	>15 years
Date in	Yes	Yes	Yes	Yes	Yes
Date out	Yes	Yes	Yes	Yes	Yes
Date death	Yes	Yes	Yes	Yes	Yes
Prescriptions					
Outpatient Rx	Yes (specialist incomplete)	Yes (specialist incomplete)	Yes	Yes (specialist incomplete)	Yes (specialist incomplete)
Coding of drugs	ATC	BNF/Multilex	ATC	ATC	ATC
Dosing regimen	Yes	Yes	No	Yes (incomplete)	Yes
Outcomes					
Hospitalizations	Yes	Yes	Yes	Yes	Yes
Outpatient diagnoses	Yes	Yes	Yes	Yes	Yes
Coding of disease	ICPC	READ	ICD-10	ICD-9 CM	ICD-10
Cause of death	Yes (from text)	If linked to death registry	Yes	No	No

*ADM = administrative; ATC = Anatomical Therapeutic Chemical; BNF = British National Formulary; ICPC = International Classification of Primary Care; MR = Medical Records*

All of the chosen databases comply with European Union (EU) guidelines on the use of medical data for medical research and have been validated for pharmaco-epidemiological research (Cazzola, 2011; Vlug, 1999).

The databases will be THIN (UK), HSD (Italy), IPCI (NL), the Aarhus University Database (DK) and SIDIAP (Spain). Table (9.4) 1 provides an overview of key elements of these databases. The total number of persons in the source population will be around 12 million as of 2012.

HSD (Italy), IPCI (Netherlands), SIDIAP (Spain) and THIN (UK) are listed under the ENCePP resources database: ([www.encepp.eu/encepp/resourcesDatabase.jsp](http://www.encepp.eu/encepp/resourcesDatabase.jsp)).

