### Selection bias

Since the study is based on electronic health care records and does not require active consent of participants, lack of participation that may lead to selection bias is not an issue in this study.

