## Information bias

Information bias may occur to not measuring correctly exposure, outcomes or co-variables.

Regarding exposure, most databases that participate in the study capture prescriptions rather than dispensings. Misclassification of exposure may occur due to lack of ‘picking up’ the prescribed medication and non-compliance. This may overestimate utilization of SR/BP and lead to non-differential misclassification of the comparative studies. Misspecification of the risk window may lead to information bias. The effect of a potential misspecification will be addressed in sensitivity analyses

Lack of recording of certain co-variables (e.g. history of fractures rather than BMD) may lead to misclassification and underestimation of the contra-indications and new indications. Similarly, lack of recording of safety events may lead to misclassification of the safety endpoints. However, previous work has shown very high validity of the coding of myocardial infarction, with positive predictive values ranging from 75% to 100% within EU-ADR Alliance partners (Coloma, 2013). DVT and VTE were only validated in some databases before and will therefore need validation in each of the data sources. Cardiovascular death may be misclassified if no autopsy is done. Validation studies will be conducted in databases where this information is not yet available (See Section 9.3.1).

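### Where GPs may no longer start strontium ranelate (Italy and Spain), recorded use can fall through lost recording, and section 9.7.2.1 does not separate this from lower true use

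*Protocol*

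**What the plan says.** **The measure.** Section 9.7.2.1 calculates monthly SR incidence by "dividing the number of new users in each month of the year by the amount of population person-time in each month". Prevalence is built the same way from patients with at least one day of SR use. Persistence and stopping are derived from gaps between prescriptions. All of this stands under the heading for RMM effectiveness, and the title page and section 8 make utilization patterns the first effectiveness objective.

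**Recording.** Table (9.4) 1 enters outpatient prescriptions as "Yes (specialist incomplete") for IPCI, THIN, HSD and SIDIAP. Aarhus alone has an unqualified yes. Section 9.3.2 accordingly limits one arm of its experienced-prescriber definition to "Therapy initiation in secondary care settings (where available: Aarhus Database").

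**Who may prescribe.** Under section 7.2, "strontium ranelate therapy should only be initiated by a physician with experience in the treatment of osteoporosis". National rules go further. Section 6 describes Italy as a country "where GPs in primary care are not allowed anymore to initiate or renew strontium ranelate treatment since December 2013" and expects few or no incident users there in the assessment period. Section 9.3.2 adds that Spanish GPs may not initiate SR but may repeat it.

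**Bias and sensitivity.** On prescriptions that are not collected or not taken, section 9.9 says "This may overestimate utilization of SR/BP". It does not mention missed specialist prescriptions. Sections 8 and 9.7.5 plan to exclude countries with legal restrictions on primary-care prescribing, and name Spain only.

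**The concern.** In four of the five sources, whether a prescription is recorded depends on who wrote it. In two of these, rules described in the protocol move SR starts away from the recorded prescribers. The Italian rule dates from December 2013, inside the transitional period; the protocol gives no exact date for Spain. An Italian patient whose treatment passes to a specialist can then look like one who stopped SR, and a new specialist patient like one who never started.

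Recorded use is reported as evidence on RMM effectiveness. If it falls between the reference and assessment periods, the plan offers no way to tell reduced use from reduced recording in the sources that hold most users. The one bias direction that section 9.9 names for utilization is the opposite one. This is not a detail left to the statistical analysis plan: the protocol itself fixes the measure, the stated bias direction and the Spain-only exclusion.

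**Working it through.** **1. Reproduce the plan's totals** (Table (9.5) 1, Total columns, 2012).
- Incident: 1,209 (HSD) + 4,008 (SIDIAP) + 514 (THIN) + 46 (Aarhus) + 42 (IPCI) = 5,819, as stated.
- Prevalent: 10,129 + 14,502 + 2,563 + 464 + 106 = 27,764, as stated.

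**2. Where the users are.**

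| Sources | Incident | Prevalent |
|---|---|---|
| Four with incomplete specialist recording | 5,773/5,819 = 99.2% | 27,300/27,764 = 98.3% |
| Italy + Spain (GP bar documented) | 5,217/5,819 = 89.7% | 24,631/27,764 = 88.7% |
| Italy alone | 1,209/5,819 = 20.8% | 10,129/27,764 = 36.5% |
| Spain alone | 4,008/5,819 = 68.9% | 14,502/27,764 = 52.2% |
| THIN + IPCI (no shift documented) | 556/5,819 = 9.6% | 2,669/27,764 = 9.6% |

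**3. What the Spain-only exclusion leaves.**
- Incident: 5,819 − 4,008 = 1,811, of which Italy has 1,209 (66.8%).
- Prevalent: 27,764 − 14,502 = 13,262, of which Italy has 10,129 (76.4%).

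Section 6 expects recorded Italian starts to become null or very low. On the 2012 mix, if they went to zero and nothing else changed, the pooled count of starts would fall from 5,819 to 4,610 (−20.8%) with Spain included. With Spain excluded it would fall from 1,811 to 602 (−66.8%). The planned exclusion therefore gives the Italian change more weight, whatever true Italian use does.

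**4. Size of a pure recording effect.** Hold true starts constant. Let s0 and s1 be the specialist share of starts before and after, and c the fraction of specialist starts that are recorded. Then

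recorded after / recorded before = [1 − s1(1 − c)] / [1 − s0(1 − c)].

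The protocol gives none of the three inputs, so all values below are assumptions.
- s0 = 30%, s1 = 80%: c = 0 gives 0.20/0.70, a fall of 71%; c = 0.5 gives 0.60/0.85, 29%; c = 0.75 gives 0.80/0.925, 14%; c = 1 gives no fall.
- s0 = 10%, s1 = 100% (a full bar on GP starts): c = 0 gives a fall of 100%; c = 0.5 gives 0.50/0.95, 47%; c = 0.75 gives 0.75/0.975, 23%.
- s1 = s0: no fall at any c.

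**5. Country by country.**
- *Italy:* initiation and renewal both leave GP care, so recorded incidence and prevalence can both drop. Section 9.7.2.1 counts an SR-free gap of 30 days as stopping, so an incident user renewed only by an unrecorded specialist counts as stopped and persistence shortens.
- *Spain:* GP repeats remain visible. A specialist start may appear late, at its first GP repeat, which raises the effective c. Ongoing use largely stays recorded.
- *UK and Netherlands:* recording is incomplete, but no change in prescriber mix is described.

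**The case against.** The strongest reply is that the measures do not remove SR from GPs. They ask for experience, and section 9.3.2 accepts "Therapy initiation in primary care by a physician with a “high number” of patients diagnosed with osteoporosis" as meeting that condition. Specialist recording is described as incomplete, not absent. Section 6 already foresees the Italian collapse and schedules a look at it for the first PSUR update. Section 9.7.2.1 stratifies every estimate by database, so Italy and Aarhus will be visible separately.

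Much of this stands, and it rules out several stronger readings that a reader might infer:
- *That recorded use falls by construction in all four GP sources.* The shift is documented for Italy and Spain only, and without a shift the effect is zero.
- *That Spanish prevalence is lost.* GP repeats keep much of it in view.
- *That the formal effectiveness test is misled by the fall in use.* The interrupted time series in section 9.7.2.2 is run on proportions among SR users. It could be affected only through which users stay recorded, and the document does not support a direction for that.
- *That section 9.9 wrongly dismisses selection bias.* Its statement, "lack of participation that may lead to selection bias is not an issue in this study", concerns participation and consent, and is fair as worded.
- *That Aarhus shows the true change elsewhere.* With 46 incident users in 2012, about four a month, it cannot.

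What the reply does not answer is that section 6 refers the Italian question to section 9.7.2.1, the measure that cannot tell lost use from lost recording. Stratification shows the drop without explaining it. The exclusion analysis omits Italy, although the Italian rule described is the stricter of the two.

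**Conclusion.** The point holds in a limited form. In Italy and Spain, with 89.7% of 2012 incident users, a fall in recorded SR incidence can reflect lost recording as well as lower use; in Italy the same applies to prevalence and persistence. The protocol reports these measures under RMM effectiveness without separating the two causes, names only the opposite bias, and plans an exclusion that leaves Italy with two thirds of the remaining incident users.

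The shares use 2012 counts as a stand-in for the whole study period. The size of the recording effect is unknown everywhere: the assumed inputs above give anything from none to a complete loss of recorded starts. For THIN and IPCI (9.6% of incident users) an effect is possible but undocumented. What is affected is the utilization objective and how it is read; the documents do not show that the interrupted time series result is biased.

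**What to change.** 1. In section 9.7.2.1, label results from IPCI, THIN, HSD and SIDIAP as primary-care-recorded SR use. State that a fall in recorded use where GPs are barred is not by itself evidence of RMM effectiveness.
2. In sections 8 and 9.7.5 and the abstract, add Italy to the legal-restriction sensitivity analysis. Report results excluding Spain, excluding Italy and excluding both.
3. In SIDIAP, add a series from the pharmacy invoicing data mentioned in section 9.4.5, if these are confirmed to cover specialist prescriptions.
4. In section 9.9, beside the over-estimation statement, add possible under-capture of SR after June 2013. Leave the participation statement as it is.
5. Show Aarhus as the one source without the specialist gap, for context only because of its size.

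The cost is wording, a few extra series and a weaker utilization claim. On 2012 counts, excluding both countries leaves 5,819 − 5,217 = 602 incident users, so that analysis will be imprecise.

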#### ***Utilization patterns patient level***

For patient level analyses SR users will be divided into incident and prevalent users. Incident users are all persons who have a first prescription for SR during the study period (one year of absence prior), prevalent users are persons who have at their first prescription during the analysis period evidence of prior prescriptions in the year before the start of the period. For prevalent users we do not know how long they have been using SR.

*Persistence of use:* persistence is the time since start of SR to the time of stopping or switching. Persistence will be calculated only for incident users.

*Stopping:* stopping is defined as lack of SR treatment within a gap of 30 days after the end of the last prescription in the treatment episode. Stopping will be calculated only for incident users.

*Switching:* switching is defined as stopping SR treatment and start of another osteoporosis treatment, during use or within a gap of 30 days after stopping. Switching will be assessed both for incident as well as prevalent users.

The gap period will be varied to 0 and to 90 days to look at the impact of the choice of gap period on these variables. Kaplan Meier models will be used to estimate persistence of use.

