## 7. RATIONALE AND BACKGROUND

### 7.1. Product

Strontium ranelate (Protelos®/ Osseor®) has been authorized since 2004 in the European Union for the treatment of osteoporosis in postmenopausal women to reduce the risk of vertebral and hip fracture. Since June 2012, strontium ranelate is also approved for the treatment of osteoporosis in adult men at increased risk of fracture. In both indications, the daily dose is 2 g daily (oral). Strontium ranelate is currently authorized in 104 countries and marketed in 91 countries.

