### 9.2.2. Study Period

The study period will start on January 1st 2004 (year of licensing) for all databases except January 1st 2006 for SIDIAP (as data is only available from 2005, and a 1-year washout is required) and will end at the most recent version of data that is available with each of the database custodians.

The study period will be divided into three analysis periods for the assessment of RMM effectiveness: up to May 2013 (*reference* period before first DHPC and revised SmPC), between June 2013 and March 2014 (*transitional* period), and after April 2014 (*assessment* period after second DHPC and new SmPC revision).

As for the safety studies, the study period will be divided in two analysis periods: 1. up to May 2013 (when the first DHPC was published, imposing new contraindications), and 2. from June 2013 (when patients with any of the new contraindications should not be prescribed SR any longer) onwards.

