### 9.3.2. Contra-indications and new indications

#### CONTRA-INDICATIONS

- History of Ischemic heart disease (IHD): myocardial infarction, angina pectoris, coronary artery bypass surgery (diagnoses or nitrate use) in year prior to SR therapy initiation.
- History of Peripheral arterial disease (PAD) in year prior to SR therapy initiation.
- History of transient ischemic attack (TIA) or stroke (ischemic or haemorrhagic) in year prior to SR therapy initiation.
- Uncontrolled hypertension, defined by MAH as the combination of the following: 1.previous diagnosis of hypertension coded in electronic medical records; 2.documented use of any anti-hypertensive therapy (either at that time or in the previous year before SR therapy initiation); and 3. at least two readings of Systolic Blood Pressure  $\geq 150$  or Diastolic Blood Pressure  $\geq 95$  mmHg recorded in the 3 months prior to SR therapy initiation.
- History of thromboembolic events (pulmonary embolism and deep venous thrombosis) in year prior to SR therapy initiation.

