#### ***Contra-indications***

Prevalence of each of the contraindications will be estimated on a patient level (new and prevalent users of SR) by age, sex, period and country. 95% Confidence Intervals will be estimated using a binomial distribution.

Interrupted time series analyses will be carried out to assess the impact of the RMM on these. Each contributing data source will be analyzed using an interrupted times series design (Kastner, 2011), using repeated measures before (up until May 2013) and after intervention (from April 2014 onwards), using a *transitional* lag time period (from June 2013 to March 2014, both included) to control for secular trends. Using this design, each database acts as its own control.

Using the interrupted times series approach, we estimate the trend in the prevalence rates in monthly intervals during the study period in the three analysis periods, and test for changes pre- and post- intervention, using the *transitional* period as a pre-specified lag time for the intervention to take effect on a) the overall (absolute rate) of outcome, and b) the slope of the trend in rates of outcome.

Segmented linear regression models will be used to estimate the monthly proportions of outcomes. Controlling for baseline level and trend, the models estimate changes in levels and trends of rates after the pre-defined interventions. The regression model includes terms to estimate the pre-existing level for each rate in the first months of the observation period (intercept), trend in the rate before the interventions were introduced, change in level of the rate during the transitional/lag time period, and change in trend after the intervention (Serumaga, 2011).

These analyses will be conducted separately for prevalent and incident SR users.

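### The prevalent-user definition leaves the reference period without prevalent users in four of five databases, and contraindications fixed at initiation cannot register disease arising on treatment

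*Protocol*

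**What the plan says.** **Who is prevalent.** Protocol 9.7.2.1 (patient-level utilization) splits SR users into incident and prevalent. Prevalent users are those who "have at their first prescription during the analysis period evidence of prior prescriptions in the year before the start of the period". It adds: "For prevalent users we do not know how long they have been using SR".

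**What an analysis period is.** Protocol 9.2.2: "The study period will be divided into three analysis periods for the assessment of RMM effectiveness: up to May 2013", followed by a transitional period (June 2013 to March 2014) and an assessment period (April 2014 onwards). On the start date: "The study period will start on January 1st 2004 (year of licensing) for all databases", with one exception: "2006 for SIDIAP (as data is only available from 2005, and a 1-year washout is required". Section 7.1 states that SR "has been authorized since 2004 in the European Union for the treatment of osteoporosis in postmenopausal women".

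**What is to be done with prevalent users.** Section 9.7.2.2 asks for the prevalence of each contraindication and each new restriction by period, and for an interrupted time series (ITS) in each database. For both sets of outcomes: "These analyses will be conducted separately for prevalent and incident SR users". The segmented model has terms for the pre-intervention level and trend, and each database serves as its own control.

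**When contraindications are measured.** Section 9.3.2 ties each one to the start of treatment, for example: "History of Peripheral arterial disease (PAD) in year prior to SR therapy initiation". The same one-year window applies to ischaemic heart disease, TIA or stroke, and thromboembolism. For blood pressure readings the window is three months before initiation.

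**A second definition of prevalent.** Section 9.5 and Table (9.5) 1 count as prevalent in 2012 those who were already users in 2011. Section 9.5 expects more than 100,000 prevalent users over the study period.

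**The concern.** Read together, 9.7.2.1 and 9.2.2 put the qualifying year for the reference period before SR could be prescribed in four databases. Those databases would have prevalent users in the transitional and assessment periods and none before the measures. The segmented model then has no pre-intervention level or trend to estimate for this group, and the period table has an empty reference column.

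At stake is the prevalent-user half of primary objectives 2 and 3 on the effectiveness of risk minimization. It is the larger half: 27,764 prevalent against 5,819 incident users in the 2012 counts.

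The measurement point is separate. Section 9.2.2 says that from June 2013 patients with a new contraindication should no longer receive SR, so continuing users are among those the measures address. A status fixed before initiation cannot change while treatment continues. The prevalent-user series could move only because people leave or join the pool, not because disease arises in those who stay.

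**Working it through.** **Step 1. The protocol's own count.** The Total column of Table (9.5) 1, prevalent users in 2012:

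10,129 (HSD) + 14,502 (SIDIAP) + 2,563 (THIN) + 464 (Aarhus) + 106 (IPCI) = 27,764, as stated.

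The male and female entries do not add to the total for HSD (613 + 9,616 = 10,229) or Aarhus (42 + 412 = 454). The Total column is used here, and nothing below turns on the difference.

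**Step 2. The qualifying window.** Under 9.7.2.1 this is the 12 months before the analysis period starts. SR was authorised in 2004. Taking 1 January 2004 as the earliest possible date is the choice most favourable to the plan.

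| Databases | Period | Qualifying window | Days with SR authorised |
|---|---|---|---|
| HSD, THIN, IPCI, Aarhus | Reference | Jan to Dec 2003 | 0 |
| SIDIAP | Reference | Jan to Dec 2005 | 365 |
| All five | Transitional | Jun 2012 to May 2013 | 365 |
| All five | Assessment | Apr 2013 to Mar 2014 | 365 |

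Any licensing date within 2004 gives the same zero in the first row.

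**Step 3. Length of the reference series.**
- Four databases, January 2004 to May 2013: 9 × 12 + 5 = 113 calendar months, none with a prevalent user under 9.7.2.1.
- SIDIAP, January 2006 to May 2013: 7 × 12 + 5 = 89 months, filled only by people prescribed SR in 2005. Nobody can join this group later.

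**Step 4. Who drops out of the prevalent group.**
- Someone who started in 2006 and was still on SR in 2012 is incident in 2006 and never a reference-period prevalent user.
- Someone who joins one of the four databases in mid-period already on SR is neither incident (no year without SR) nor prevalent (no 2003 prescription).

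**Step 5. Conflict with the feasibility count.** Users counted as prevalent in 2012, inside the reference period, in the four databases where 9.7.2.1 gives zero:

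10,129 + 2,563 + 464 + 106 = 13,262, and 13,262 / 27,764 = 47.8%.

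The other 14,502 (52.2%) are in SIDIAP, where only those prescribed SR in 2005 would qualify.

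**Step 6. The contraindication anchor.** No arithmetic applies. Section 9.3.2 looks back from initiation and gives no other anchor for prevalent users. A myocardial infarction in the third year of continuous use falls after the window and is not counted in any month, in any database. Section 9.7.2.1 also treats the duration of use, and hence the start date, as unknown for this group.

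**The case against.** The strongest reply is that the period in 9.7.2.1 could be a month or a year. The Abstract promises contraindication prevalence by year and month for prevalent users, 9.7.2.2 works in monthly intervals, and 9.7.2.1 itself computes population prevalence of use per month or year. The feasibility count is the same formula with the period set to calendar 2012. So a rolling definition was probably meant. That stands as a view of intent and makes the repair easy. It does not rescue the text: 9.7.2.1 speaks of the analysis period, and for this part of the study 9.2.2 gives that term only the three fixed blocks. Because a standardized script is to build the output tables for all five databases (9.6.5), the intended unit has to be written down. Nor is this detail left for a statistical analysis plan. The protocol states a definition, and a later plan would have to contradict it.

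Three stronger inferences are tempting, and the documents do not support them.

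- *The prevalent-user analysis is empty everywhere, or the effectiveness analysis fails as a whole.* SIDIAP has 2005 prescriptions and therefore some reference-period prevalent users. The incident-user series do not use this definition; the 2006 starter above is counted there.
- *Contraindications cannot be dated for any prevalent user.* The statement about unknown duration reads as a caution. In four databases the study period begins in the licensing year, so the start is on record for many later prevalent users. What remains is that a status fixed at initiation cannot change in a continuing user, even when the date is known.
- *A repaired definition recovers all 113 months.* The earliest months after licensing have few or no prior users under any definition, and SIDIAP has at most 89 months.

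**Conclusion.** The point holds on the text, in two parts.

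1. The 9.7.2.1 definition, applied to the fixed reference period of 9.2.2, yields no reference-period prevalent users in HSD, THIN, IPCI and Aarhus, and a closed 2005 group in SIDIAP. The prevalent-user ITS and before/after prevalences of 9.7.2.2 have no baseline in four of five databases. The definition also conflicts with the calendar-year one in 9.5, which gives 27,764 prevalent users in 2012, 13,262 of them in those four databases.
2. In all five databases, contraindications anchored to initiation leave out disease that arises during treatment in continuing users.

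The first part assumes that the analysis period has the meaning 9.2.2 gives it, and that there was no SR prescribing before authorisation in 2004. The second needs neither assumption. The empty count does not touch the incident-user analyses.

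**What to change.** **Define prevalent use on a rolling basis in 9.7.2.1.** A prevalent user in month m has SR use in month m and at least one SR prescription in the 365 days before month m. For yearly and period tables use the calendar-year equivalent. Apply the rule identically in the reference, transitional and assessment periods, and reconcile it with the definition in 9.5.

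**Give prevalent users their own anchor in 9.3.2.** Assess contraindications at the first SR use or prescription in month m, with the look-back lengths already set there: one year, and three months for blood pressure. Keep those lengths fixed. Using all available history for prevalent users only would lengthen ascertainment with calendar time (SIDIAP data begin in 2005). Recorded contraindications could then rise artificially and bias the trend that the ITS estimates, and the two user groups would be measured differently.

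**Keep the initiation-based outcomes of 9.7.2.2** (such as experienced prescriber and not first line) for prevalent users whose initiation date is on record, and state that these cannot change in a continuing user.

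**Cost.** Protocol wording and a script parameter. Section 6 plans data collection from April 2015, so the change can be made before extraction. The protocol should say that the first months after licensing will still have few or no prevalent users.
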